#### 9.3 Characteristics of an Adverse Event

# 9.3.1 Relationship to Study Intervention

To assess relationship of an event to study intervention, the following guidelines are used:

- 1. Related (Possible, Probable, Definite)
  - a. The event is known to occur with the study intervention.
  - b. There is a temporal relationship between the intervention and event onset.
  - c. The event abates when the intervention is discontinued.
  - d. The event reappears upon a re-challenge with the intervention.
- 2. Not Related (Unlikely, Not Related)
  - a. There is no temporal relationship between the intervention and event onset.
  - b. An alternate etiology has been established.

# 9.3.2 Expectedness of SAEs

The NIDCR Medical Monitor and the Study PI will be responsible for determining whether an SAE is expected or unexpected. An adverse event will be considered unexpected if the nature,

severity, or frequency of the event is not consistent with the risk information previously described for the intervention.

## 9.3.3 Severity of Event

The following scale will be used to grade adverse events:

- 1. Mild: no intervention required; no impact on activities of daily living (ADL)
- 2. Moderate: minimal, local, or non-invasive intervention indicated; moderate impact on ADL
- 3. Severe: significant symptoms requiring invasive intervention; subject seeks medical attention, needs major assistance with ADL

# 9.4 Reporting Procedures

## 9.4.1 Unanticipated Problem Reporting to IRB and NIDCR

Incidents or events that meet the OHRP criteria for unanticipated problems require the creation and completion of an unanticipated problem report form. As per OHRP recommendation, the following information will be included when reporting an adverse event, or any other incident, experience, or outcome as an unanticipated problem to the IRB:

- appropriate identifying information for the research protocol, such as the title, investigator's name, and the IRB project number;
- a detailed description of the adverse event, incident, experience, or outcome;
- an explanation of the basis for determining that the adverse event, incident, experience, or outcome represents an unanticipated problem;
- a description of any changes to the protocol or other corrective actions that have been taken or are proposed in response to the unanticipated problem.

To satisfy the requirement for prompt reporting, unanticipated problems will be reported using the following timeline:

- Unanticipated problems that are serious adverse events will be reported to the IRB and to NIDCR within 1 week of the investigator becoming aware of the event.
- Any other unanticipated problem will be reported to the IRB and to NIDCR within 2 weeks of the investigator becoming aware of the problem.
- All unanticipated problems should be reported to appropriate institutional officials (as
  required by an institution's written reporting procedures), the supporting agency head (or
  designee), and OHRP within one month of the IRB's receipt of the report of the problem
  from the investigator.

All unanticipated problems will be reported to NIDCR's centralized reporting system via Rho Product Safety:

- Product Safety Fax Line (US): [name]
- Product Safety Fax Line (International): [contact]
- Product Safety Email: rho [contact]

General questions about SAE reporting can be directed to the Rho Product Safety Help Line (available 8:00AM – 5:00PM Eastern Time):

US: [name]

International: [contact]

# 9.4.2 Serious Adverse Event Reporting to NIDCR

Any AE meeting the specified Serious Adverse Event criteria will be submitted on an SAE form to NIDCR's centralized safety system via Rho Product Safety. This report may be sent by fax or email. Once submitted, Rho Product Safety will send a confirmation email to the investigator within 1 business day. The investigator should contact Rho Product Safety if this confirmation is not received. This process applies to both initial and follow-up SAE reports.

SAE Reporting Contact Information:

Product Safety Fax Line (US): [name]

Product Safety Fax Line (International): [contact]

Product Safety Email: rho\[contact]

General questions about SAE reporting can be directed to the Rho Product Safety Help Line (available 8:00AM – 5:00PM Eastern Time):

US: [name]

International: [contact]

The study clinician will complete a Serious Adverse Event Form and submit via fax or email within the following timelines:

- All deaths and immediately life-threatening events, whether related or unrelated, will be recorded on the Serious Adverse Event Form and submitted to Product Safety within 24 hours of site awareness.
- Serious adverse events other than death and immediately life-threatening events, regardless of relationship, will be reported by fax within 72 hours of site awareness.

All SAEs will be followed until resolution or stabilization.

## 9.4.3 Reporting of SAEs and AEs to FDA

Not applicable.

# 9.4.4 Events of Special Interest (if applicable)

Not applicable.

# 9.4.5 Reporting of Pregnancy

In the highly unlikely event that a 6-12 year-old is found to be pregnant during the course of the study, it will be noted in the database and the subject will be discontinued from the study.

# 9.5 Halting Rules

Safety findings that would temporarily suspend enrollment and/or study interventions until a safety review is convened include SAEs. A safety review will be conducted if there are a large number of SAE's overall, a large number of occurrences of a particular type of SAE, severe AEs/reactions, or increased frequency of events.

Subsequent review of serious, unexpected problems by the Medical Monitor, CSOC, IRB, the sponsor(s), or the relevant local regulatory authorities may also result in suspension of additional enrollment as well as further trial interventions.

### 10 STUDY OVERSIGHT

In addition to the Pl's responsibility for oversight, study oversight will be under the direction of a Clinical Study Oversight Committee (CSOC) composed of members with expertise to oversee the study including expertise in autism spectrum disorders, occupational therapy, pediatric dentistry, and statistical analysis of clinical trials data. The CSOC will meet to review the clinical protocol before study recruitment begins, and then approximately annually to assess unanticipated problems, study conduct, and progress. If major concerns arise, more frequent meetings may be held. The CSOC will operate under the rules of an NIDCR-approved charter that will be approved at the organizational meeting of the CSOC. At this time, most data elements that the CSOC needs to assess will be clearly defined. The CSOC will provide recommendations to the NIDCR. In addition to the CSOC, an internal system for monitoring adverse events will be set up in conjunction with the study's database system. As per NIDCR guidelines, members of the CSOC will be appointed by NIDCR.

### 11 CLINICAL SITE MONITORING

Clinical site monitoring is conducted to ensure that the rights of human subjects are protected, that the study is implemented in accordance with the protocol and/or other operating procedures, and that the quality and integrity of study data and data collection methods are maintained. Monitoring for this study will be performed by NIDCR's Clinical Research Operations and Management Support (CROMS) contractor. The monitor will evaluate study processes and documentation based on NIDCR standards and the International Conference on Harmonisation (ICH), E6: Good Clinical Practice guidelines (GCP).

Details of clinical site monitoring will be documented in a Clinical Monitoring Plan (CMP) developed by the CROMS contractor, in collaboration with the NIDCR Office of Clinical Trials and Operations Management (OCTOM) and the NIDCR Program Official. The CMP will specify the frequency of monitoring, monitoring procedures, the level of clinical site monitoring activities (e.g., the percentage of subject data to be reviewed), and the distribution of monitoring reports. Some monitoring activities may be performed remotely, while others will take place at the study site(s). Staff from the CROMS contractor will conduct monitoring activities and provide reports of the findings and associated action items in accordance with the details described in the CMP. Documentation of monitoring activities and findings will be provided to the site study team, the study PIs, OCTOM, and the NIDCR. The NIDCR reserves the right to conduct independent audits as necessary.

### 12 STATISTICAL CONSIDERATIONS

# 12.1 Study Hypotheses

**Primary Objective:** To compare children's physiological anxiety (EDA - primary outcome) during the dental cleaning in SADE vs. RDE.

**Hypothesis 1:** Children will exhibit less physiological anxiety (SCL and NS-SCR frequency) during routine dental care in the SADE condition compared to the RDE.

**Secondary Objective 2:** To compare children's negative behavioral responses (behavioral distress, perception of pain, sensory discomfort - secondary outcomes) during dental cleanings in SADE vs. RDE.

**Hypothesis 2:** Children will exhibit fewer negative behavioral responses during routine dental care in the SADE condition compared to the RDE.

**Secondary Objective 3:** To test the degree to which physiological anxiety mediates the SADE intervention's effects on children's negative behavioral responses.

**Hypothesis 3:** Physiological anxiety mediates the effect of the intervention in decreasing child negative behavioral responses.

**Secondary Objective 4:** To test the degree to which specific child characteristics moderate the SADE intervention's effects on children's physiological and negative behavioral responses during dental cleaning.

**Hypothesis 4:** The magnitude of physiological and negative behavioral response change in the SADE, relative to the RDE, will be greater in children with ASD with increased sensory over-responsivity, high dental anxiety, greater ASD severity, lower IQ, and/or younger age.

**Secondary Objective 5:** To compare the SADE intervention to the RDE on quality of care, cost-effectiveness, and potential cost savings of dental cleaning.

**Hypothesis 5a:** The SADE intervention, compared to the RDE, is cost-effective and results in decreased overall costs.

**Hypothesis 5b:** The SADE intervention, compared to the RDE, results in improved quality of care as evidenced by thoroughness of dental cleaning.

# 12.2 Sample Size Considerations

The R34 pilot study provided estimates of effect size used for sample size calculations, which ranged greatly across measures for children with ASD. Figure 1 shows the N required to detect a difference between dental environments based on the results from the pilot study. As these effect sizes were typically smaller than those found by Shapiro et al., $^{50-51}$  they represent a more conservative estimate of sample size, and have the benefit of being specific to the population and measures proposed here. Sample size estimates were computed to detect the effect of the repeated measurement environment for outcomes specified in the primary objective, with EDA being the primary outcome (Hyp 1) and distress behavior, perception of pain, and sensory discomfort secondary, with 1-=0.80 and -=0.025 (Hyp 2). In the R34 pilot study, the effect sizes for EDA difference between environments ranged from Cohen's d = 0.44-0.46 (see Figure

1). The effect size of the environment difference for sensory discomfort and pain intensity were large (d's = 0.69 and 0.62, respectively), while distress behavior measure effects were small (d's ranging from 0.11 to 0.23), likely due to the restricted range of answers in those measures. Attrition in the pilot data was extremely low (2%), however the more conservative attrition estimate of 10% was used for these calculations. Thus we will recruit 220 children with ASD, anticipating having repeated measures on 165. This N will allow for the detection of a within group change attributable to environment of Cohen's d = 0.22. Figure 1 shows the estimated sample size, including the effect sizes from the R34; as indicated, our target sample size, after attrition, should have sufficient power to detect differences in our primary outcome.

[figure not shown]

Figure 1. Sample size estimates based on ASD participants of R34 Pilot and Feasibility Study

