#### 5 STUDY ENROLLMENT AND WITHDRAWAL

The study target sample size is 220 English- and Spanish-speaking children with ASD. We anticipate a 4:1 ratio of boys to girls in the ASD group based on current statistics (CDC, 2014) and consistent with recruitment in our R34 study. Based on our results from our R34 SADE study, we anticipate that the ethnic and racial backgrounds of our sample will mirror the general population of CHLA patients. Specifically, we expect more than half of individuals to be of Hispanic/Latino origin with a preponderance of Caucasian children.

Based on our R34-funded pilot study, we plan to recruit children with ASD from CHLA Dental Clinic. Each week, study staff will review the electronic health records of the list of patients scheduled for a dental cleaning in the CHLA Dental Clinic. For those appearing to meet inclusion criteria for the study, study staff will contact the parents or guardians and invite participation in the study.

Based on our pilot study, we found that it may be difficult to recruit a sufficient number of children with a range of ASD severity. Therefore, for this study we plan to recruit children from multiple sites including CHLA (Dental Clinic, USC UCEDD, Boone Fetter Clinic, AltaMed), and the Los Angeles Unified School District. See Section 5.3 for greater detail about these sites.

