#### Retention

To aid in retention of study participants, a series of steps will be taken. Reminder phone calls, texts, and/or e-mails for meetings and dental visits will occur (based on stated parent preference). Additionally, the first meeting, consisting of the consent process and survey completion, will take place at the family home or CHLA, whichever is more convenient for the family. Utilizing these strategies in the R34 pilot study, we were able to retain 98% of our participants. However, since not all participants will be patients in the CHLA Dental Clinic, we expect there may be a larger loss. We have allowed for a loss of 10%, targeting a sample of 165 participants with complete data from a recruited sample of 220 children with ASD.

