# 12.4 Final Analysis Plan

Descriptive statistics will be performed for all variables of interest to describe the participant population at baseline, including attrition rate and missing data, to compare those randomized to SADE first vs. those randomized to RDE first. We anticipate a low attrition rate (~10%) and will impute missing data for intent-to-treat analyses using Markov Chain Monte Carlo (MCMC)

imputation with multiple values imputer for each missing value averaged for an estimation for analyses. Bivariate associations between outcomes (physiological anxiety and children's negative behavioral responses), environment (SADE or RDE), and covariates (age, gender, order of visit, autism severity, IQ, and sensory sensitivity) will be described. The primary objective of determining difference between dental environments will be tested using intent-to-treat models examining the within-subject factor of dental environment (SADE vs RDE) using repeated measures ANCOVA for each outcome. *A priori* covariates include age (continuous), randomized order of visit, gender, and temperature. Other participant characteristics that are unbalanced between order of visits will be included as covariates *ad hoc*.

The secondary objective of examining the mediating effect of physiologic response on behavioral outcomes will be tested by first examining the bivariate relationships between EDA and behavioral outcomes, and then adding EDA estimates (SCL and NS-SCR) to models of dental environment difference on behavioral outcomes, and examining the change in the within group coefficients. A change in coefficient >15% will be considered evidence of mediation. While we have several outcomes, we specify only one mediator, thus we will apply a rational approach to examination of multiple outcomes, and will assess the fidelity of our study by estimating effect sizes (Cohen's d) of the dental environment before and after the mediation factors are assessed to confirm that statistical results were supported by clinical relevance of findings. If physiological anxiety does mediate the environment's effect on negative behavioral responses, we anticipate that the anticipated effect of environment will be eliminated once we add in EDA to the models specified in Hypothesis 2. Analyses will be performed using SPSS (v.22); a priori two-sided  $\square = 0.05$ .

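### A 10% loss does not take 220 recruited children to 165 with complete data: 10% leaves 198, and 165 of 220 is a 25% loss

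*Combined protocol and SAP*

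**What the plan says.** The recruitment target is fixed in section 5: "The study target sample size is 220 English- and Spanish-speaking children with ASD".

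Section 5.3, under Retention, gives the loss, the completers and the recruits together: "We have allowed for a loss of 10%, targeting a sample of 165 participants with complete data from a recruited sample of 220 children".

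Section 12.2 reports 2% attrition in the pilot, then says "however the more conservative attrition estimate of 10% was used for these calculations", and draws the conclusion "Thus we will recruit 220 children with ASD, anticipating having repeated measures on 165". The next sentence is "This N will allow for the detection of a within group change attributable to environment of Cohen's d = 0.22". The section ends by claiming that "our target sample size, after attrition, should have sufficient power to detect differences in our primary outcome".

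Section 12.4 repeats the assumption: "We anticipate a low attrition rate (~10%) and will impute missing data for intent-to-treat analyses". It sets the significance level for the analyses: "Analyses will be performed using SPSS (v.22); a priori two-sided" 0.05. Section 12.2 gives power of 0.80 and a level of 0.025. The symbols beside that 0.025 are not legible in the text available, and no sidedness is given.

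**The concern.** In both 5.3 and 12.2 the 10% is the only loss named, and 12.2 presents 220 and 165 as following from it. A 10% loss does not connect those two numbers. Either the allowance for loss, the number of completers or the number recruited is misstated.

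Three things depend on which it is: the benchmark against which actual attrition will be judged (22 children lost or 55), the description of attrition as low that introduces the imputation in 12.4, and a reader's ability to rebuild the sample-size justification.

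**Working it through.** **Inputs.** 220 recruited (5, 5.3, 12.2); 165 with complete data or repeated measures (5.3, 12.2); 10% loss (5.3, 12.2, and about 10% in 12.4); power 0.80 and detectable d = 0.22 (12.2); two-sided 0.05 (12.4); 0.025, sidedness not given (12.2); pilot electrodermal effect d = 0.44 to 0.46 (12.2).

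**Step 1: the attrition arithmetic.**
- Completers from 220 at 10% loss: 220 × (1 − 0.10) = 198, not 165. The gap is 198 − 165 = 33.
- Loss implied by 165 of 220: 1 − 165/220 = 25.0%, or 55 children rather than 22.
- Recruits needed for 165 completers at 10% loss: 165/0.90 = 183.3, so 184.
- The cruder inflation 165 × 1.10 = 181.5 gives 182. Applying 10% twice gives 220 × 0.81 = 178, and three times gives 160. None of these links 220 to 165.
- Two pairs do return exactly 220: 165/0.75 and 198/0.90.

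**Step 2: which N the d = 0.22 fits.** Assume a paired t-test with d standardised by the SD of within-child differences. Power is the probability that a noncentral t variable with N − 1 degrees of freedom and noncentrality d√N exceeds the critical value.

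The plan's own figure first. At N = 165, d = 0.22 and two-sided 0.05, the noncentrality is 0.22 × √165 = 2.826, the critical t is 1.975, and power is 80.2%. At N = 164 power is just under 80%, so 165 is the smallest N that reaches 80%. One-sided 0.025 gives the same result.

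| N | Level | Power for d = 0.22 | Detectable d at 80% power |
|---|---|---|---|
| 165 | two-sided 0.05 (or one-sided 0.025) | 80.2% | 0.219 |
| 165 | two-sided 0.025 | 71.3% | 0.242 |
| 198 | two-sided 0.05 (or one-sided 0.025) | 86.9% | 0.200 |
| 198 | two-sided 0.025 | 79.8% | 0.2205 |

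Two rows round to the stated 0.22: 165 at two-sided 0.05, and 198 at two-sided 0.025. The number 198 appears nowhere in the documents, whereas in 12.2 the sentence giving d = 0.22 directly follows the 165.

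**Step 3: the primary outcome.** For d = 0.44, 80% power needs 43 children at two-sided 0.05 or 52 at two-sided 0.025. Power is at least 99.96% in all four rows above. As a harsher check, standardise d by the raw-score SD with zero correlation between visits, so that the effect on the difference scale is 0.44/√2 = 0.311. Power is then 97.8% (two-sided 0.05) or 95.8% (two-sided 0.025) at N = 165, and 99.2% or 98.3% at N = 198.

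**The case against.** The strongest defence is that the protocol describes losses other than dropout. Under 7.3, a child whose diagnosis is not confirmed on the ADOS-2 leaves the study after enrolment. Under 5.5.1, a child who cannot tolerate the electrodes may be withdrawn. The 5.3 target is for complete data, which can be stricter than retention. Together these could take 198 down to 165. This is possible, but it is not stated. It needs a further loss of 33/198 = 16.7%, which no section quantifies. Both 5.3 and 12.2 describe the 220 as children with ASD, and 12.2 derives its figures from the 10% alone. If this is what was meant, the plan has to say so, and the fix below allows for it.

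A second defence is that the practical effect is close to nil. That stands. Section 12.2 claims sufficient power only for the primary outcome, and step 3 supports the claim.

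A reader might go further in three ways that the documents do not support.

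- That nobody can tell which N the d = 0.22 rests on. The wording points to 165, and 165 matches at the one level whose sidedness is legible.
- That the study has only 71% power for d = 0.22. This requires N = 165 and a two-sided 0.025, and the text does not establish the second.
- That 0.025 in 12.2 and 0.05 in 12.4 are a second contradiction. A one-sided 0.025 and a two-sided 0.05 give the same detectable d, so this is a point to clarify.

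**Conclusion.** Wrong as written, minor. The arithmetic is exact and needs no assumption: the stated loss is 10% and the implied loss is 25%, a difference of 33 children.

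That the 10% is the figure at fault is likely, not proven. It rests on the order of the sentences in 12.2 and on the match of 165 with d = 0.22 at two-sided 0.05, under a paired t-test with d on the SD of within-child differences. The competing match, 198 at two-sided 0.025, keeps it short of proof.

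The error lies in the documentation of the sample size. It does not threaten the primary comparison if the pilot effect is about right.

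**What to change.** Restate one set of figures in 5.3, 12.2 and 12.4. Either:

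- (a) 220 recruited; 25% total loss, naming any losses expected beyond the 10% dropout, such as ADOS-2 non-confirmation or unusable electrodermal recordings; 165 with both cleanings; detectable d = 0.22 at 80% power and two-sided 0.05. Or
- (b) 220 recruited; 10% loss; 198 with both cleanings; detectable d = 0.20 at 80% power and two-sided 0.05.

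One clarification belongs with this: state whether the 0.025 in 12.2 is one- or two-sided. If it is two-sided, the detectable d is 0.24 at N = 165 or 0.22 at N = 198, and the chosen set should say so.

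The cost is wording only. The COVID-19 note in 7.3 records that all participants had been recruited and had completed Visits 1 to 3 by March 2020, so recruitment, visits and analyses are unchanged. The trade-off under (a) is that the plan must own a 25% planned loss, and 12.4 can no longer describe the expected attrition as about 10% without separating dropout from the other losses.
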